#### **4.3. Randomisation**

Eligible patients will be randomly assigned to receive either *Octaplex* or FP. Randomisation lists using a permuted-block, randomisation scheme (stratified by site) will be prepared by the biostatistician. Sealed randomisation envelopes based on the randomisation lists will then be provided to the blood banks/pharmacies of the participating centres who will be responsible for providing the IMP.

Patients will be identified using a sequential numbering system within the centre. Randomisation will then be performed in sequential order of the patient IDs.

#### **4.4. Study Assessments**

An overview of all assessments during the study is contained in Table 1 of the study protocol. For further details, observations and procedures per visit are described in section 6.1 and study assessments are described in sections 7.1 to 7.3 of the study protocol.

### **5. Endpoints**

#### **5.1. Primary Endpoint**

1. Comparison of haemostatic treatment response to *Octaplex* versus FP, defined as 'effective' if no additional haemostatic intervention, such as administration of any systemic haemostatic agents (including platelets, cryoprecipitate, fibrinogen concentrate, activated recombinant factor VII, other coagulation factor products or a second dose of IMP) or any haemostatic interventions (including surgical re-opening for bleeding) is required from 60 minutes to 24 hours after initiation of the first dose of IMP.

#### **5.2. Secondary Endpoints**

##### *Efficacy endpoints*

1. Comparison of global haemostatic response to *Octaplex* versus FP, defined as 'positive' if no additional haemostatic intervention (as per the primary endpoint) is required and haemoglobin levels decrease by <30% (after accounting for red cell transfusions) from 60 minutes to 24 hours after initiation of the first dose of IMP.
2. Comparison of the total amount of chest tube drainage at 12 and 24 hours after chest closure between the *Octaplex* and FP groups.

3. Comparison of the incidence of severe to massive bleeding, using a modification of the universal definition of perioperative bleeding (UDPB) in cardiac surgery and its individual components during the first 24 hours after start of surgery, after the end of CPB and after IMP initiation, between the *Octaplex* and FP groups.
4. Comparison of the mean number of total allogeneic blood components – including red cells, platelets and all (IMP and non-IMP) FP – administered during the first 24 hours after the end of CPB, between the *Octaplex* and FP groups.
5. Comparison of the mean number of total non-IMP allogeneic blood components – including red cells, platelets and non-IMP FP – administered during the first 24 hours after the end of CPB, between the *Octaplex* and FP groups.
6. Comparison of the mean number of total non-IMP allogeneic blood components – including red cells, platelets, cryoprecipitate and non-IMP FP – administered during the first 24 hours and 7 days after IMP initiation, between the *Octaplex* and FP groups.
7. Comparison of the mean number of individual allogeneic blood components – including red cells, platelets, cryoprecipitate and non-IMP FP – administered during the first 24 hours and 7 days after the start of surgery, after the end of CPB and after IMP initiation, between the *Octaplex* and FP groups.
8. Comparison of the incidence of transfusion of individual allogeneic blood components – including red cells, platelets, cryoprecipitate and non-IMP FP – during the first 24 hours and 7 days after the start of surgery, after the end of CPB and after IMP initiation, between the *Octaplex* and FP groups.
9. Comparison of the incidence of administration of non-IMP coagulation factor products – including fibrinogen concentrate and activated recombinant factor VII – during the first 24 hours and 7 days after the start of surgery, after the end of CPB and after IMP initiation, between the *Octaplex* and FP groups.
10. Comparison of the incidence of intracerebral haemorrhage during the first 24 hours after start of surgery, after the end of CPB and after IMP initiation between the *Octaplex* and FP groups.
11. Comparison of the incidence of gastrointestinal haemorrhage during the first 24 hours after start of surgery, after the end of CPB and after IMP initiation between the *Octaplex* and FP groups.
12. Comparison of the incidence of surgical re-exploration during the first 24 hours after start of surgery, after the end of CPB and after IMP initiation between the *Octaplex* and FP groups.
13. Comparison of the change in INR, from within 30 minutes before to within 60 minutes after the initiation of IMP administration, between the *Octaplex* and FP groups; INR reduction will be considered successful if the magnitude of the reduction is  $>1.0$  or the post-treatment level drops below 1.5.
14. Comparison of the changes in other coagulation parameters, including prothrombin time (PT), activated partial thromboplastin time (aPTT), fibrinogen activity, ROTEM EXTEM CT and maximum clot firmness (MCF) and platelets, from within 75 minutes before to within 75 minutes after the initiation of IMP administration, between the *Octaplex* and FP groups.
15. Comparison of time elapsed from initiation of the first dose of IMP to arrival at the ICU room between the *Octaplex* and FP groups.

#### *Safety endpoints*

All adverse events (AEs) and serious AEs (SAEs) will be collected from beginning of surgery (defined as entry into operating room) to postoperative day (POD)-30.

1. Comparison of the incidence of serious treatment-emergent adverse events (TEAEs), individually and as composite where appropriate (e.g., TEEs and major adverse cardiac events [MACE]), between the *Octaplex* and FP groups.
2. Comparison of the duration of mechanical ventilation (measured as duration of ventilation and ventilator-free days) up to POD-30 between the *Octaplex* and FP groups.
3. Comparison of the duration of ICU stay up to POD-30 between the *Octaplex* and FP groups.
4. Comparison of the duration of hospitalisation up to POD-30 between the *Octaplex* and FP groups.
5. Comparison of the incidence of death up to POD-30 between the *Octaplex* and FP groups.
6. Comparison of the number of days alive and out of hospital at POD-30 between the *Octaplex* and FP groups.

## 6. Analysis Populations

### US Study Sites:

At the US study sites, voluntarily given, written informed consent will be obtained from the patient before any study-related procedures are conducted.

### Canadian Study Sites:

At the Canadian study sites, informed consent will be obtained from the patient or the patient's legally authorised representative (LAR) as soon as possible after surgery. If neither the patient nor the LAR is reachable for consent during the follow-up period, a family member who is not a LAR is to be provided with an opportunity to object to the patient's participation in the study.

Due to the emergency nature of the condition being studied (i.e., bleeding during surgery) the trial will include only patients who are incapable of providing informed consent at the time the therapy is needed and in whom delays in obtaining surrogate consent can be severely detrimental to their well-being. Thus, this study qualifies for alteration to consent requirement before randomisation, in accordance with Article 3.7A of the 2018 Tri-Council Policy Statement on the Ethical Conduct for Research Involving Humans. Patient or LAR consent from all patients, including those untreated, will be obtained at the earliest possible opportunity after surgery.

It is not possible to predict which patients will bleed due to coagulation factor deficiency, and once identified, any delays in therapy will lead to patient harm. The entire process from termination of CPB to administration of the blood products is around 50 minutes. However, the time frame for therapy decision, and consequently for seeking consent from a LAR for the patient to participate in the trial (meaning consent to randomisation and all study procedures thereafter), is even shorter, as it consists of the 5–10 minutes in which coagulation assays are reviewed and a call is placed to the blood bank to order coagulation factors. Even if it were possible to contact a LAR to seek consent during this time, the acuity of the situation would likely be highly stressful to the LAR, which could preclude them from effectively making an informed decision regarding consent. These factors make it essentially impossible to obtain prospective informed consent from a LAR during the surgery.

As a rule, only data from randomised and treated patients with informed consent will be analysed. Consented and randomised but untreated patients will not be included in the efficacy or safety analyses but will be followed for 30 days to determine between-group comparability in baseline characteristics and outcomes.

To ensure that the safety reporting is complete, all haemostatic therapy and SAE data will be collected in cases where consent for remaining in the study cannot be obtained from Canadian sites due to logistical issues (e.g., patient died and a legally authorised representative could not be reached) and REB approval is obtained to collect the information. For Canadian patients who refuse consent, only treatment allocation data will be collected, and patients will not be included in any analyses.

Hence, the disposition of patients will be displayed according to the following analysis populations:

- All Patients population (APP)
  - Patients consented at the US study sites (US APP)
  - Patients randomised at the Canadian study sites (Canadian APP)
- Failed Consent Patients (FCP) population
- Full Analysis Set (FAS) population
- Safety (SAF) population
- Per-Protocol Set (PPS)

A final decision about the classification of protocol deviations and their consequences regarding assignment of patients to analysis populations will be made during the data review meeting prior to the final analyses. All protocol deviations documented during the conduct of the study or identified at the data review process prior to database lock will be reviewed and classified as minor or major and with respect to their significance for the planned analyses. This classification of protocol deviations is the joint responsibility of the clinical project manager, the study statistician, and Octapharma's responsible medical expert, and will be agreed and documented before the database is locked and the statistical analyses are performed.

### **6.1. All Patients Population (APP)**

The AP population will include all patients regardless of the consent status. This population will only be used for displays of patient disposition. This population will also be separated by the country where patients are enrolled, i.e., into the US APP, containing all patients screened and consented at US sites, and the Canadian APP, containing all patients randomised to treatment at the Canadian sites.

### **6.2. Failed Consent Patients (FCP) Population**

The FCP population will consist of all randomised Canadian patients who receive at least one treatment with either PCC or FP for whom consent cannot be obtained (due to logistical reasons and if approved by the REBs). This population will only be used for displays of haemostatic therapy and serious adverse events.

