3.2 Overall Study Design and Plan

This is a multicentre, randomised, active-control, prospective, Phase 3 study in adult cardiac surgery patients. Approximately 500 patients will be randomised at approximately 12 hospitals (10 in Canada and two in the United States), and the study will require

approximately two years to complete. The study is planned to start in quarter 4, 2022 and to be completed in quarter 4, 2024.

The study will include adult (≥ 18 years old) patients who undergo cardiac surgery on CPB and require coagulation factor replacement due to bleeding post-CPB and after adequate reversal of heparin with protamine (as assessed by the surgical staff based on clinical and laboratory criteria) during surgery, and who have a known (e.g., as indicated by INR) or suspected coagulation factor deficiency. Patients will be randomised to receive either 4-factor PCC (*Octaplex*) or FP when the blood bank/pharmacy receives the first order for coagulation factor replacement and determines patient eligibility with the study team based on the study inclusion and exclusion criteria.

Following confirmation of eligibility, the technologist will randomise the patient to PCC or FP according to the randomisation and dosing schedule and prepare and release the IMP in a tamper sealed container. Operating room personnel will remain blinded until the decision to administer the IMP is made.

[figure not shown]
IMP can be administered if bleeding is severe enough to necessitate IMP (meaning at least a grade 2 level [moderate] bleeding according to the validated Bleeding Severity Scale [78]), heparin is adequately reversed (confirmed by the return of post-protamine activated clotting time [ACT] to within 10% of pre-pump ACT) and INR is ≥ 1.5 . IMP can also be administered if bleeding is severe enough to require urgent therapy, in which case treatment can be initiated irrespective of the INR value. Once the decision is made to administer the IMP, the administering clinician will break the seal on the container, carry out routine safety checks and initiate IMP administration according to the weight-based dosing recommendations.

The recommended initial dose for *Octaplex* will be 1500 IU for patients weighing ≤ 60 kg and 2000 IU for patients weighing >60 kg. The recommended initial dose for FP will be 3 U for patients weighing ≤ 60 kg and 4 U for patients weighing >60 kg.

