9.2.1 Populations for Analysis

The full analysis set (FAS) will consist of all consented and randomised patients who receive any amount of the intervention, which will serve as the primary analysis set. A supporting efficacy analysis will be performed for the per-protocol set (PPS), which will exclude all patients with major deviations (e.g., patients who receive an IMP different to the IMP assigned by randomisation; patients who receive <50% of the planned dose; and patients who significantly violate inclusion/exclusion criteria). Randomised but untreated patients will not be included in the efficacy or safety analyses, but will be followed for 30 days to determine between-group comparability in baseline characteristics and outcomes.

A final decision about the classification of protocol deviations and their consequences regarding assignment of patients to analysis populations will be made during the data review meeting prior to the final analyses. All protocol deviations documented during the conduct of the study or identified at the data review process prior to database lock will be reviewed and classified as minor or major and with respect to their significance for the

planned analyses. This classification of protocol deviations is the joint responsibility of the clinical project manager, the study statistician, and Octapharma's responsible medical expert, and will be agreed and documented before the database is locked and the statistical analyses are performed.

The safety analysis population (SAF) will be identical to the FAS. In addition, to ensure that the safety reporting is complete, all haemostatic therapy and SAE data will be collected in cases where consent for remaining in the study cannot be obtained from Canadian sites due to logistical issues (e.g., patient died and a legally authorised representative could not be reached) and REB approval is obtained to collect the information. For Canadian patients who refuse consent, only treatment allocation data will be collected, and patients will not be included in any analyses.

The following subgroups will be analysed: sex (male/female); urgency (elective/non-elective surgery); and complexity (simple/complex surgery [procedures other than isolated ACB, single valve or repair of atrial septal defect]). Moreover, the impact of CPB duration on effectiveness will be evaluated by assessing treatment effect based on CPB duration increments.

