### **6.3. Full Analysis Set (FAS) Population**

The full analysis set (FAS) will be defined according to the intention-to-treat (ITT) principle and will consist of all randomised patients who provide consent and receive any amount of the intervention.

The FAS will serve as the primary analysis set. For patients who withdraw consent, data will be used up until the time consent is withdrawn.

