#### **6.4. Safety (SAF) Population**

The safety analysis population (SAF) will be identical to the FAS.

For patients who refuse consent only treatment allocation data will be collected and they will not be included in any of the analyses.

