## 11. Safety Analysis

All safety analyses will be based on the FAS population. If the SAF population differs from the FAS population, then only AE information will additionally be displayed for the SAF.

All AEs and SAEs will be collected from beginning of surgery (defined as entry into OR) to POD-30.

The analysis of safety will study the following endpoints:

1. Comparison of the incidence of serious treatment-emergent adverse events (TEAEs), individually and as composite where appropriate (e.g., TEEs and MACE), between the *Octaplex* and FP groups.
2. Comparison of the duration of mechanical ventilation (measured as duration of ventilation and ventilator-free days) up to POD-30 between the *Octaplex* and FP groups.
3. Comparison of the duration of initial ICU stay up to POD-30 between the *Octaplex* and FP groups.
4. Comparison of the duration of hospitalisation up to POD-30 between the *Octaplex* and FP groups.
5. Comparison of the incidence of death up to POD-30 between the *Octaplex* and FP groups.
6. Comparison of the number of days alive and out of hospital at POD-30 between the *Octaplex* and FP groups.

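### The planned between-arm estimates of death and serious TEAEs leave out treated Canadian patients whose consent could not be obtained, although their SAE data are collected

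*SAP*

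**What the plan says.** The trial is largely Canadian: Protocol 3.2 gives "approximately 12 hospitals (10 in Canada and two in the United States". At the Canadian sites consent is deferred. SAP 6 (Canadian Study Sites) has it sought from the patient or the patient's "legally authorised representative (LAR) as soon as possible after surgery". If neither can be reached during follow-up, a family member who is not a representative is given the chance to object.

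The analysis sets follow from consent:

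- SAP 6.3: the FAS "will consist of all randomised patients who provide consent and receive any amount of the intervention".
- SAP 6.4: "The safety analysis population (SAF) will be identical to the FAS".
- SAP 6.2: randomised and treated Canadian patients whose consent cannot be obtained for logistical reasons, subject to ethics board approval, form the FCP set. "This population will only be used for displays of haemostatic therapy and serious adverse events".
- SAP 6 and 6.4: for patients who refuse, only the treatment allocation is kept.

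Protocol 9.2.1 gives the purpose of collecting data on the failed-consent patients: "to ensure that the safety reporting is complete, all haemostatic therapy and SAE data will be collected". SAP 6 repeats this. Both use the example of a patient who died and whose representative could not be reached.

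For the analysis, SAP 11 says "All safety analyses will be based on the FAS population" and lists serious TEAEs and death to POD-30 among the comparisons. SAP 11.1 specifies a risk ratio with a 95% confidence interval for death.

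**The concern.** When consent is sought after treatment, failure to obtain it can itself result from the outcome. A patient who dies early cannot consent, and if no representative is found the patient leaves the FAS. The documents' own example describes exactly this. The set used to compare deaths can therefore lose patients because they died.

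PCC is a procoagulant, and Protocol 1.1 acknowledges a possible higher thrombotic risk at high doses. Thirty-day death and serious TEAEs are therefore central safety outcomes. Some of the earliest fatal events could be on file but absent from every planned between-arm estimate.

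**Working it through.** **Step 1: can a failed-consent patient enter any between-arm safety estimate?**

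- The death risk ratio and serious-TEAE comparison use the FAS (SAP 11, 11.1).
- The FAS needs consent (SAP 6.3; Protocol 9.2.1 agrees), so these patients are not in it.
- SAP 11 would also display AEs for the safety set if it differed from the FAS. By definition the two are identical (SAP 6.4), so this adds nobody.
- The sensitivity analyses in SAP 10.4 concern the primary endpoint only.
- The FCP set is for displays only (SAP 6.2).

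The answer is no. The data would nevertheless exist where the ethics board agrees, because an event that results in death is an SAE (Protocol 7.3.3).

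**Step 2: the efficacy side.** SAP 10.1, Table 1, sets response to No when a patient dies before the end of the 24-hour period. A failed-consent patient who dies in that period is outside the FAS, so the rule is never applied to that death. This concerns only FCP deaths before 24 hours.

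**Step 3: denominators.** The documents give no expected mortality and no FCP count. The only figure to anchor on is 205 evaluable patients per arm (Protocol 3.3.1.5). It reproduces from Protocol 9.1 (70% versus 65%, margin 0.10, one-sided 0.025, power 90%):

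n = (1.960 + 1.282)² × (0.70×0.30 + 0.65×0.35) / (0.05 + 0.10)² = 10.51 × 0.4375 / 0.0225 ≈ 204.3, rounded up to 205.

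**Step 4: illustrative effect on the death risk ratio.** Assumptions: 10 deaths per arm in the FAS; a PCC and b FP patients added from the FCP set, all of whom died.

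RR = [(10+a)/(205+a)] / [(10+b)/(205+b)]

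SE(log RR) = √[1/(10+a) − 1/(205+a) + 1/(10+b) − 1/(205+b)]; 95% CI = exp(log RR ± 1.96 SE)

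- FAS alone: (10/205)/(10/205) = 1.00; SE 0.436; CI 0.43-2.35.
- a=3, b=1: (13/208)/(11/206) = 0.0625/0.0534 = 1.17; SE 0.398; CI 0.54-2.55.
- a=1, b=3: (11/206)/(13/208) = 0.85; CI 0.39-1.86.
- a=2, b=2: RR stays 1.00, but overall mortality moves from 20/410 = 4.9% to 24/414 = 5.8%.

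With four such deaths, the share of all deaths in treated patients left out is 4/24 = 17%.

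**Step 5: sensitivity to the assumptions.**

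- *FAS deaths.* Adding 2+1 gives (6/207)/(5/206) = 1.19 with 4 FAS deaths per arm, 1.09 with 10, and (17/207)/(16/206) = 1.06 with 15.
- *Trial size.* Adding 4+1 at about 5% mortality gives 1.25 (0.58-2.70) with 205 per arm. With 500 per arm, the maximum of 1000 evaluable patients, it gives 1.11 (0.66-1.86).
- *Survivors in the FCP set.* If survivors split between the arms as the deaths do, the shift shrinks slightly. With 3+1 deaths and 3+1 survivors, (13/211)/(11/207) = 1.16 instead of 1.17.

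**The case against.** The strongest reply is that this is a declared rule with its own reporting route. SAP 6 says that, as a rule, only consented and treated patients are analysed, and the estimand in SAP 10.1 names valid consent in its population. The FCP set exists so that these patients' SAEs are shown, and patient listings carry treatment arm and analysis set (SAP 13). Completeness of safety reporting is arguably met by display; neither document promises a pooled comparison. The illustrative shifts are also small beside the FAS interval of 0.43-2.35. All of this stands. It limits the size of the point but does not supply the missing estimate.

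A second reply concerns the remedy. FAS plus FCP is still selected by consent, because refusers stay out. It may also be enriched for deaths: only haemostatic therapy and SAE data are named as collected for the FCP set, so the 30-day status of unreachable survivors may be unknown. This stands too. It is why the pooled result should be supportive and reported with counts.

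Three stronger readings are tempting and are not supported:

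- *Every early Canadian death is excluded.* No. A representative may consent, and such a patient stays in the FAS. Treated patients who consent and later withdraw also remain, with data used up to withdrawal (SAP 6.3).
- *Fatal events are concealed.* No. They are displayed, and a reader could count them by arm by hand.
- *The plan favours PCC, or the non-inferiority result is unsafe.* No by-arm information is given, so the direction is unknown. The death risk ratio is an estimate, not a confirmatory test.

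**Conclusion.** The point holds as a gap in the safety estimates. No planned between-arm estimate of death or serious TEAEs includes treated patients in the FCP set, and membership of that set can depend on the outcome being compared. This sits uneasily with the stated reason for collecting their SAE data.

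The group is probably small, and the documents do not allow its size or its split by arm to be computed. Under the assumptions in Step 4, a 3-to-1 split in either direction moves the risk ratio from 1.00 to 1.17 or 0.85, well inside the FAS interval; an even split does not move it. No formal decision changes. The addition is worth making because the data will be to hand, and specifying the estimate now avoids a choice after the results are seen.

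One question stays open in the SAP: whether a case in which a family member who is not a representative does not object enters the FAS or the FCP set.

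**What to change.** Keep the FAS analyses as planned and amend SAP 6.2, 6.4, 11 and 11.1 as follows:

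1. Add a pre-specified supportive comparison, by randomised arm, of death to POD-30 and serious TEAEs in FAS plus FCP, wherever the ethics board permits this use. Give the SAP 11.1 death risk ratio with 95% CI for both sets side by side.
2. Report the numbers of FCP and refusing patients by arm and, within the FCP set, the number with unknown 30-day vital status by arm.
3. State which set receives a patient when neither the patient nor the representative is reached and a family member does not object.
4. State the limits of the pooled set: it still omits refusers and may over-represent deaths.

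The cost is SAP wording and a few tables. The first item depends on ethics board permission, since approval is already needed to collect these data.
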